3 BACKGROUND AND RATIONALE

3.1 Background and Rationale

In recent years, economic evaluations have become increasingly important because of the growing emphasis on cost containment. The evaluation of both costs and benefits allows more comprehensive consideration of the value of a particular intervention.

In cost-utility studies, benefits are measured in healthy year equivalents, usually expressed by qualityadjusted life-years (QALYs) and the incremental cost-effectiveness ratio (ICER) [1, 2]. The ICER is the difference in costs between two interventions, divided by the difference in their effect expressed in QALYs. There is no explicit threshold defining a cost-effective intervention. Thresholds have been suggested being below 50'000 USD - 150'000 USD for high-income countries [2, 11]. In addition to direct healthcare expenses, the costs associated with loss of productivity lead to substantial economic consequences for the patient, the employer, and society. Studies have shown, that costs associated with loss of productivity are considerably higher than direct medical costs [3]. Here, we see a great potential of the Touch® implant. A first analysis of our registry data showed that in average patients return to work 20 days after surgery. In contrast, data of a previous study investigating loss of productivity in patients after resection-suspension-interposition (RSI) arthroplasty showed a considerably longer absence from work of 54 days [4]. The difference in the return to work is also confirmed by other studies that even showed considerably longer absences from work after CMC I surgery [12-14], with, however, the time of sick leave also being shorter for patients after implant arthroplasty compared to RSI arthroplasty (4.7 vs. 8.9 months) [14]. Furthermore, the clinical and patient-reported outcomes in the short-term seem to be favourable for patients with a Touch® implant compared to RSI arthroplasty, once again undermining the potential of this specific implant.

Lastly, there is a risk that health insurances will not pay the Touch® implant, because it is more expensive than a RSI arthroplasty. However, if we could prove that other associated costs, such as loss of productivity, are significantly lower with the Touch® implant, we will have strong arguments against such decisions.

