4.3 Secondary Objective

As a secondary objective we want to determine whether direct medical costs are higher with the Touch® implant compared to RSI arthroplasty. Cost-effectiveness regarding pain ADL will be evaluated as the difference in costs over the difference in pain ADL between both interventions. We will analyse return to work after surgery in both groups. Lastly, we will compare the clinical and patient-reported outcomes after surgery for both groups.

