5.2 Secondary Outcomes

The following secondary outcomes will be measured at each timepoint (at baseline and 6 weeks, 3 months and 1 year after surgery):

Range of motion

Flexion and extension of the MCP and thumb Interphalangeal (IP) joint will be measured with a goniometer. The evaluation of active thumb opposition is based on the Kapandji index, ranging from 1 to 10 [8]. Patients try to touch their fingers with the tip of the thumb. The score is 1 when patients are able to touch only the lateral side of the index finger and 10 when they can reach the volar crease of the hand.

Grip strength and key pinch

Grip strength of the affected hand will be measured with the help of a JAMAR dynamometer. Thumb key pinch will be measured with a pinch gauge. The testing position is standardized as recommended by the American Society of Hand Therapists [30].

The brief Michigan Hand Outcomes Questionnaire (MHQ)

The brief MHQ measures hand function and shows good measurement properties [7, 31]. The score ranges from 0 to 100 with higher scores indicating better hand function. We will use the German version of the brief MHQ [32].

Pain

The pain level of the thumb at rest and during daily activities will be documented using a Numeric Rating Scale (NRS; 0 = no pain, 10 = worst pain).

Satisfaction

At follow-up, there will be three additional questions about satisfaction:

- How is your operated thumb in general compared to before the surgery?
 - Response options: Much better (score 5), slightly better (score 4), unchanged (score 3), slightly worse (score 2), much worse (score 1)
- How satisfied are you with the treatment result of the operation on your thumb?
 - Response options: Very satisfied (score 5) / satisfied (score 4) / neither satisfied nor dissatisfied (score 3) / dissatisfied (score 2) / very dissatisfied (score 1)

- In hindsight, would you decide to have this operation again?
 - Response options: No (score 1), Not sure (score 2), Yes (score 3)

Physical work demands

To estimate the physically demanding work, the patients will be asked about their physical activity during work as well as the presence of strenuous work [9].

- Do you have to use your hands a lot during your regular work?
 - Response options: Yes / No
- Do you regularly have to carry / hold loads with your hand or work using the strength of your hands?
 - o Response options: No / A little / Sometimes / A lot

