10.4.3 Secondary Analysis

Categorical outcomes (e.g. radiological findings) will be described by proportions and frequency counts at follow-up time points.

Continuous outcomes (e.g. Brief MHQ or Pain) will be analysed by mixed model considering the effect of time and reported per examination time by their mean and standard error.

Cost-effectiveness analysis

The incremental cost-effectiveness ratio (ICER) will be calculated as:

Cost _{Touch®} - Cost _{RSI Arthroplastik} ADL pain score_{Touch®} - ADL pain score_{RSI Arthroplastik}

Costs will combine direct (inpatient and outpatient) and indirect (productivity losses) costs.

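### The secondary pain cost-effectiveness ratio divides by Touch minus RSI on a lower-is-better pain scale, so its sign is opposite to cost per point of pain relief

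*Protocol*

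**What the plan says.** Protocol section 4.3 makes the pain ratio part of the secondary objective: "Cost-effectiveness regarding pain ADL will be evaluated as the difference in costs over the difference in pain ADL between both interventions". It gives no direction for the difference.

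Section 10.4.3 gives the direction by printing a formula. The numerator is the cost of Touch minus the cost of RSI, and the denominator is "ADL pain score_{Touch®} - ADL pain score_{RSI Arthroplastik". On the numerator it adds: "Costs will combine direct (inpatient and outpatient) and indirect (productivity losses) costs".

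Section 5.2 defines the pain scale, at rest and in daily activities, as "NRS; 0 = no pain, 10 = worst pain".

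Section 10.4.2 uses the same Touch-minus-RSI layout for the primary ratio, with QALYs in the denominator. Nowhere does the protocol reverse the pain score, define it as relief, or say how a negative ratio is to be read.

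**The concern.** A cost-effectiveness ratio is normally read as a price per unit of health gained, which requires a denominator that is positive when the new treatment is better. QALYs meet that requirement in 10.4.2. The pain score does not, because a benefit of Touch lowers it. The QALY layout appears to have been reused for pain without allowing for the direction of the scale.

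What is at stake is how a stated secondary objective is read. The two ratios would probably be reported close together and may both be called ICERs. For the same favourable clinical result they would carry opposite signs, and a reader who applied the QALY convention to the pain ratio would misplace Touch.

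**Working it through.** The protocol states no numerical value or planning figure for the pain ratio, so there is none to reproduce. The check is of signs.

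**Inputs**
- Scale direction: lower is better (section 5.2).
- Numerator: direct plus indirect costs (section 10.4.3). Its sign is open. Section 3.1 says insurers may refuse the implant "because it is more expensive than a RSI arthroplasty". It also reports return to work after 20 days with Touch, while earlier RSI data "showed a considerably longer absence from work of 54 days", a gap of 54 - 20 = 34 days in favour of Touch.
- Expected outcome: section 3.1 describes short-term clinical and patient-reported results as favouring Touch, so less pain with Touch is the direction to plan for.
- Illustration (assumed, not from the protocol): a cost difference of CHF 2,000 and pain scores of 1 and 2, a gap of 1 point. The signs do not depend on these values.

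**Formulas**
- dC = cost Touch - cost RSI; dP = pain Touch - pain RSI.
- As written: R = dC / dP.
- Per point of pain relief: R* = dC / (pain RSI - pain Touch) = dC / (-dP) = -R.

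So R and R* always have the same size and opposite signs, whenever dC and dP are not zero.

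| Touch compared with RSI | dC | dP | As written, R | Per point of relief, R* | True position of Touch |
|---|---|---|---|---|---|
| Dearer, less pain | +2,000 | -1 | -2,000 | +2,000 | trade-off: pays for relief |
| Cheaper, less pain | -2,000 | -1 | +2,000 | -2,000 | dominant |
| Dearer, more pain | +2,000 | +1 | +2,000 | -2,000 | dominated |
| Cheaper, more pain | -2,000 | +1 | -2,000 | +2,000 | trade-off: saves at the cost of pain |

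**Reading the table**
- In the second and third rows the best and worst outcomes for Touch both show as +2,000, which under the usual convention is an ordinary price per unit gained.
- In the first row a real price for pain relief shows as a negative number.
- The QALY ratio has a positive denominator when Touch is better. It is positive for a dearer, better Touch and negative for a cheaper, better one. That matches R*, not R.

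**If the score is taken as a change from baseline.** Define relief as baseline minus follow-up. The Touch-minus-RSI difference in relief is (base Touch - follow-up Touch) - (base RSI - follow-up RSI) = (follow-up RSI - follow-up Touch) + (base Touch - base RSI). With equal baselines this is RSI minus Touch at follow-up, so the orientation is correct. The printed formula names a score, however, not a reduction.

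**The case against.** The ratio as written is a legitimate quantity: CHF per point on the pain score. Its absolute size is right, and section 5.2 states the scale direction, so an analyst who keeps that in mind can read it correctly. No decision rule is attached to it. The thresholds in section 3.1 are discussed for the QALY-based ratio, and none is given for pain. An analysis plan that is not shown could also settle the details. All of this bears on how serious the matter is. It does not remove the defect, because the protocol prints a specific formula whose orientation conflicts with its own scale.

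A reader might infer that a dearer, less painful Touch would be reported as dominant. The documents do not support that. A negative ratio alone cannot separate dominant from dominated. Read by its components, a higher cost with a negative apparent effect, that case would look dominated. Either misreading is possible and neither is certain.

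A reader might also count the lack of baseline adjustment as a second error. The protocol does not give the time point for this ratio, and such detail may properly be left to the analysis plan. Baseline pain is scheduled for Touch patients and the cohorts are not randomised. That is a reason to consider a change-based denominator, but it is not further evidence that the formula is wrong.

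**Conclusion.** The concern holds as an orientation error in one secondary analysis. The formula in 10.4.3 gives the opposite sign to cost per point of pain relief in every quadrant, and this follows from the formula and the scale definition without any numerical assumption. The CHF 2,000 and 1 point serve only as illustration.

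The conclusion assumes that the ADL pain score is the NRS score itself, as the wording says. If improvement from baseline was meant, the sign would be right, but the protocol does not say so.

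It would go too far to infer that the trial's main conclusion is at risk. The QALY ratio in 10.4.2 is correctly oriented, and the sample size in 10.2 rests on EQ-5D-5L scores, not on pain. The magnitude of the pain ratio is also unchanged. The point deserves correction before analysis but does not threaten the primary result.

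**What to change.** In section 10.4.3, write the denominator as pain relief. Either of two forms will do:
- ADL pain score RSI minus ADL pain score Touch; or
- the Touch-minus-RSI difference in pain reduction from baseline, which takes account of unequal starting pain in non-randomised cohorts. The baseline score is already scheduled for Touch patients. This form also needs it in the existing RSI data, which should be confirmed first.

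Label the result as CHF per additional NRS point of pain relief. Add one sentence saying that the cost difference and the pain difference are reported beside the ratio, so that negative values are read by quadrant. Section 10.4.2 describes no bootstrap or quadrant reporting that could be borrowed by cross-reference, so the sentence has to stand on its own.

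Section 4.3 states no direction and needs no change beyond staying consistent with the corrected formula. The first form costs one formula and one sentence, with no new data and no effect on the primary analysis or the sample size.

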10.4.4 Interim analyses

The Schulthess Klinik will need to provide KeriMedical with an analysis of loss of productivity six months after surgery for 40 patients.

10.4.5 Safety analysis

Complications occurring within a postoperative study period of 1 year will be analysed according to their class and time of occurrence, severity and relation-to-implant.

10.4.6 Deviation(s) from the original statistical plan

Any deviations from the planned analyses will be justified and documented and an amendment will be sent to the CEC if required. After approval of the CEC the adapted statistical plan will be used.

10.5 Handling of missing data and drop-outs

The reasons for patient dropout and lost to follow-up status will be documented. If patients drop out before surgery, they will be replaced. If they drop out after the surgery, they won't be replaced, and all available data will be used for analysis. It is not planned to replace missing data for this analysis. However, if many missing data occur and if they are missing at random (MAR), they will be replaced using multiple imputation.

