8.2 Compliance with study intervention

Post-surgery the patients will schedule their first two follow-ups. This will be done by the surgeon's secretary office. A study assistant will make sure the patients are invited again for the later 1-year follow-up and will schedule the visit during the follow-up range.

A patient is non-compliant if he/she either doesn't fill out the questionnaires or doesn't show up for the clinical examinations. Non-compliance and the reason thereof will be documented electronically. The study assistant will follow up on non-compliant patients if some or all of the questions on a questionnaire weren't filled out or if the patient doesn't show up for the examinations. If the participant does not want to participate in the study anymore, he will be documented as a dropout. If the participant didn't fill out the questionnaires at the right time or for some reason couldn't come for the examination but still wants to participate in the study, we will report his data as missing for a single timepoint.

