10.4.2 Primary Analysis

Quality of life

The EQ-5D-5L responses will be converted into utilities ranging from -0.66 (lowest QoL) to 1(highest QoL) according to the German value set [34]. The change in quality of life measured by the EQ-5D utility index from before to 1 year after surgery will be analysed by the paired t-test. Sample size will be sufficient to waive the requirement for Normal distribution of the outcome parameter.

Only one look at the data will be performed at the end of follow-up and significance level will be set at 5%.

Cost-utility analysis / Quality-Adjusted Life Years (QALYs)

A population preference-based value index from Germany will be used to calculate Quality-Adjusted Life Years (QALYs) for each patient. The gain in QALYs of Touch patients compared to RSI patients will be evaluated.

QALYs will be calculated as "utilities" multiplied with "time units" under this utility. Then, a cost-utilityratio will be calculated as: Additional costs per additional QALY (Quality adjusted life year). The incremental cost-utility ratio will be calculated as the difference in costs over the difference in Quality-Adjusted Life Years (QALYs) between both interventions [28].

> Cost _{Touch®} - Cost _{RSI} Arthroplastik QALYS_{Touch®} - QALYS_{RSI} Arthroplastik

Sensitivity analyses will be performed considering:

- Different assumptions of gain in QALYs
- Different assumptions for calculation of indirect costs (productivity losses)
- Different assumptions about the direct medical costs.

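### Section 10.5 makes imputation conditional on an undefined amount of missing data and on MAR, which the data cannot establish, so the handling of missing data in the primary ICER would be chosen after the data are seen

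*Protocol*

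**What the plan says.** Section 10.5 sets the default: "It is not planned to replace missing data for this analysis". It then adds the exception: "if many missing data occur and if they are missing at random (MAR), they will be replaced using multiple imputation". For patients who drop out after surgery, "they won't be replaced, and all available data will be used for analysis". Section 8.2 covers a patient who stays in the study but misses a questionnaire or examination: "we will report his data as missing for a single timepoint".

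The primary analysis in section 10.4.2 uses a German value set, which "will be used to calculate Quality-Adjusted Life Years (QALYs) for each patient", with each QALY built as utility multiplied by the time spent at it. The EQ-5D change "from before to 1 year after surgery will be analysed by the paired t-test". Under section 5.1, direct costs come from the hospital accounting system, and productivity losses from the WPAI combined with questions on work status and income. The study schedule places these questionnaires at baseline, 6 weeks, 3 months, 6 months and 1 year.

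**The concern.** The rule has two triggers, and neither can be applied as written. The first has no number. Section 10.2 already expects 15% dropout, and nothing says whether that would count as many. The second asks whether the data are MAR. That depends on how missingness relates to the values that were not observed, so the observed data cannot answer it.

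By the time anyone decides whether the triggers are met, both versions of the ICER can be computed. The decision bears on the primary outcome, and on the productivity component on which the rationale for the implant largely rests. The implant's manufacturer part-funds the study (sections 2.5 and 13.1), so a rule that needs no judgement after the data are in would protect the result better.

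**Working it through.** **1. What the default does to each component of the ICER**

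| Component | Source | Effect of one missed questionnaire with no imputation |
|---|---|---|
| QALY | EQ-5D-5L at five timepoints, summed as utility × time for each patient | One-year total cannot be formed without filling the gap |
| Productivity cost | WPAI, work status and income at the same timepoints | One-year total has a gap, although the reported duration of absence from work may cover part of it |
| Direct hospital cost | Hospital accounting system | None |
| External therapy sessions | Patient report × mean session cost | The report may be lost |
| Paired t-test of EQ-5D change | Baseline and 1 year | Patient lost if either of these two scores is missing |

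Section 10.4.1 defines the primary dataset as all eligible, enrolled patients operated on and scheduled for the implant. A patient with a missed form belongs to that set but contributes no one-year QALY under the default. Section 10.4.3 gives the secondary continuous outcomes a mixed model, which can use partial records. The primary ICER has no such provision.

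**2. Assumptions needed**

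A comparison of group means among patients with complete series needs completeness, within each group, to be unrelated to the QALY or productivity loss itself. Multiple imputation under MAR lets completeness depend on what was observed, such as baseline utility or the utility at an earlier visit. The default is therefore the more demanding choice.

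**3. How many Touch patients could be affected**

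The documents give no missing rate per visit, so p is an assumption, taken as independent across visits. Starting from 80 × 0.85 = 68 patients, the number with all five questionnaires is 68 × (1 − p)^5:

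- p = 2%: 68 × 0.904 = 61
- p = 5%: 68 × 0.774 = 53
- p = 10%: 68 × 0.590 = 40

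If the same patients tend to miss several forms, more complete series remain than this.

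**4. Whether power is the problem**

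The plan's own figure first. Inputs from section 10.2: 42 controls, mean 0.91, SD 0.09; Touch mean 0.96, SD 0.05; two-sided alpha 0.05; Satterthwaite t test. With 68 Touch patients, SE = √(0.09²/42 + 0.05²/68) = 0.01515, df ≈ 56.9, noncentrality 0.05/0.01515 = 3.30, power 0.9003. With 67 it is 0.8997, so 68 is reproduced, and 68/0.85 = 80.

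This test needs only the 1-year score, so only 1-year missingness enters it:

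| 1-year scores missing (assumed) | Both groups: Touch / RSI | Power | Touch only: Touch / RSI | Power |
|---|---|---|---|---|
| 5% | 64.6 / 39.9 | 0.885 | 64.6 / 42 | 0.898 |
| 10% | 61.2 / 37.8 | 0.867 | 61.2 / 42 | 0.896 |

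The loss is small. The protocol defines no power for the ICER or for total QALYs.

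**The case against.** The protocol nowhere says complete cases. It promises to use all available data, and section 8.2 treats a missed form as one missing timepoint, not as exclusion of the patient. An analyst could average utilities at each visit over whoever responded and build a group-level QALY from those means. That would honour the promise, but it is not the calculation that section 10.4.2 describes, "to calculate Quality-Adjusted Life Years (QALYs) for each patient", and unadjusted visit means also need more than MAR. Dropping the patient remains an inference, but it follows from the planned per-patient quantity.

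The SAP is not at hand, and a threshold for many, the imputation model and its predictors are the kind of detail a protocol may leave to it. This stands for those details. It does not help with the second trigger, because no SAP can turn MAR into a condition that is checked against the data. The MAR clause could be read as merely naming the assumption under which imputation would be done, but as worded it is a condition for doing it.

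There are safeguards. Under section 8.2 the study assistant follows up incomplete questionnaires, and under section 10.4.6 deviations must be justified and documented. The first reduces missing data. The second does not apply, because either choice is within the plan.

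A reader might go further in three ways that the documents do not support:

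- **A large loss of power.** This comes from putting the number of patients with every visit complete into the sample-size test. That test needs only the 1-year score.
- **Heavy loss among the controls.** Section 10.2 reports a 1-year mean and SD for the 42 RSI patients, which reads as scores already in hand. Their completeness at other visits is not stated.
- **A bias in favour of the implant.** It is plausible that patients who recover slowly return fewer forms, but this is a guess. The ICER uses differences between groups, and similar selection in both could partly cancel.

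**Conclusion.** The point holds in a limited form. Section 10.5 states a rule, and the rule cannot be applied without judgement after the data are seen: one trigger is undefined and the other cannot be established from the data. In effect the default removes patients with a missed form from the QALY and productivity components of the primary ICER, on assumptions stronger than those of MAR-based imputation.

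The size of the bias cannot be given, because the documents report no missing rates per visit, and its direction is unknown. Under the assumed 2% to 10% missing per timepoint, between about 61 and 40 of the 68 retained Touch patients would have a complete series. Power for the planned EQ-5D contrast stays at 0.867 or above in the scenarios shown. The rule should be changed, although its practical effect will be small if few forms are missed.

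**What to change.** Rewrite the last two sentences of section 10.5 as follows:

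- State MAR as the working assumption of the primary analysis, and delete the two conditions.
- Make visit-level multiple imputation, run separately by group, the primary handling of missing utilities and productivity costs. Use baseline utility, demographics, physical work demands and the observed utilities and productivity costs as predictors. Calculate QALYs and cost totals after imputation.
- Report the complete-case result and one MNAR shift as sensitivity analyses, and add them to the list in section 10.4.2, which does not mention missing data.

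The cost is one paragraph and a little more Stata programming. If little is missing, the result barely changes.
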